### 8.8.4. Plasma PD Parameters

Plasma PD parameters will be computed for PK/PD sub-study patients only. Plasma PD parameters for plasma VAP-1/SSAO activity and methylamine will be calculated from the individual plasma VAP-1/SSAO activities and methylamine concentrations using a non-compartmental approach for Week 0/Day 1, Week 6, and Week 12. Week 0/Day 1 and Week 6 will include pre-dose and all post dose assessments prior to the next dose. Week 12 will include pre dose and all post dose assessments. The actual PD sampling times will be used for the PD analysis. If actual PD sampling times are missing, nominal times will be used.

[Table 8](#) and [Table 9](#) present the plasma PD parameters to be calculated.

**Table 8: VAP-1/SSAO Plasma PD Parameters**

Abbreviation	Parameter Definition
AAUC tau	Area under curve for VAP-1/SSAO activity, calculated separately for the value, change from baseline, and percent change from baseline over a dosing interval, i.e. from 0 to 24 hours, calculated using the linear trapezoidal rule.

Abbreviation	Parameter Definition
$A_{\min}$	Minimum observed VAP-1/SSAO activity, calculated separately for the value, change from baseline, and percent change from baseline, obtained directly from the plasma VAP-1/SSAO activity time profiles. In the case where multiple minimums are of equal magnitude, the earliest minimum values will be reported as $A_{\min}$ .
$A_{\max}$	Maximum observed VAP-1/SSAO activity, calculated separately for the value, change from baseline, and percent change from baseline, obtained directly from the plasma VAP-1/SSAO activity time profiles. In the case where multiple maximums are of equal magnitude, the earliest maximum values will be reported as $A_{\max}$ .
$AT_{\min}$	Time of the minimum observed VAP-1/SSAO activity, calculated separately for the value, change from baseline, and percent change from baseline, obtained directly from the plasma VAP-1/SSAO activity time profiles. In the case where multiple minimums are of equal magnitude, the time of the earliest minimum will be reported as the $AT_{\min}$ .
$AT_{\max}$	Time of the maximum observed VAP-1/SSAO activity (and separately, change and percent change from baseline), obtained directly from the plasma VAP-1/SSAO activity and methylamine concentration-time profiles. In the case where multiple maximums are of equal magnitude, the time of the earliest maximums will be reported as the $AT_{\max}$ .
$AT_{\text{last}}$	Time of the last quantifiable VAP-1/SSAO activity value
$A_{\text{avg}}$	Average observed VAP-1/SSAO activity, calculated separately for the value, change from baseline, and percent change from baseline at steady state (Week 6 and Week 12 only)

**Table 9: Methylamine Plasma PD Parameters**

Abbreviation	Parameter Definition
AUC tau	Area under curve for methylamine concentration (and separately, change and percent change from baseline) over a dosing interval, i.e. from 0 to 24 hours, calculated using the linear trapezoidal rule.
C min	Minimum observed methylamine concentration (and separately, change and percent change from baseline) obtained directly from the plasma methylamine concentration-time profiles. In the case where multiple minimums are of equal magnitude, the earliest minimum values will be reported as C min .
C max	Maximum observed methylamine concentration (and separately, change and percent change from baseline) obtained directly from the plasma methylamine concentration-time profiles. In the case where multiple maximums are of equal magnitude, the earliest maximum values will be reported as C max .
T min	Time of the minimum observed methylamine concentration (and separately, change and percent change from baseline), obtained directly from the plasma and methylamine concentration-time profiles. In the case where multiple minimums are of equal magnitude, the time of the earliest minimum will be reported as the T min .
T max	Time of the maximum observed methylamine concentration (and separately, change and percent change from baseline), obtained directly from the plasma methylamine concentration-time profiles. In the case where multiple maximums are of equal magnitude, the time of the earliest maximums will be reported as the T max .
T last	Time of the last quantifiable methylamine concentration
C avg	Average observed methylamine concentration (and separately, change and percent change from baseline) at steady state (Week 6 and Week 12 only)

#### **8.8.4.1. PD Parameter Data Handling**

#### **8.8.4.2. Calculation of AUC**

AUCs will be calculated using linear trapezoidal rule. For any partial AUC determination (i.e., AUC over a dosing interval), nominal time will generally be used for the end of the interval.

The minimum requirement for the calculation of AUC will be the inclusion of at least three consecutive plasma VAP-1/SSAO activity or methylamine concentrations above the LLOQ.

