#### **8.8.4.3. Statistical Methods for PD Parameters**

Plasma PD parameters will be summarized by treatment group using descriptive statistics (number of non-missing observations, arithmetic mean, SD, median, Q1, Q3, minimum, maximum, geometric mean, and geometric CV%).

For the calculation of summary statistics, all NR and not calculated (NC) values in a data series will be set to missing.

Analyses of pre-dose/trough values for plasma VAP-1/SSAO activity ( $A_{avg}$  and  $A_{min}$ ) and methylamine ( $C_{avg}$  and  $C_{max}$ ) at Week 0/Day 1, Week 6, and Week 12 will be carried out using an ANCOVA model with the PD parameter as the dependent variable including treatment group as a fixed effect and baseline VAP-1/SSAO activity or methylamine concentration as a covariate. The model will be carried out separately for the PD parameter based on the VAP-1/SSAO activity and methylamine value, change from baseline, and percent change from baseline. The estimates of LS means, SE, and 90% and 95% CIs will be presented by treatment group. Estimates of the LS mean difference for each pairwise comparison will be presented with associated the standard error of the difference, and 90% and 95% CIs of the difference.

The distribution of parameter values will be evaluated visually for normality assumptions. If normality assumptions are violated, first the data will be natural log transformed and the log transformed data evaluated for normality. If the log transformed data are normally distributed, the same ANOVA model described above will be used.

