#### 8.8.4.4. Dose Response

If Part 2 enrolls, dose-response may be evaluated, if the data warrants, based on the pairwise comparisons of pre-dose/trough values for plasma VAP-1/SSAO activity ( $A_{avg}$  and  $A_{min}$ ) and methylamine concentration ( $C_{avg}$  and  $C_{max}$ ) from the ANCOVA models specified above (Section 8.8.4.3). In addition, pre-dose/trough VAP-1/SSAO activity ( $A_{avg}$  and  $A_{min}$ ) and methylamine concentration ( $C_{avg}$  and  $C_{max}$ ) will also be plotted by treatment group based on values, change from baseline, and percent change from baseline.

Dose response will also be evaluated using a REML based MMRM. The dependent variable will be the percent change (separately for change) from baseline for plasma VAP-1/SSAO activity and methylamine. The model will include the following fixed effects:

- Treatment group (4 levels: placebo [0 mg], 4 mg, 10 mg, 20 mg)
- Categorical time
- Treatment group by time interaction
- Baseline value

An unstructured covariance model will be used. If the computational algorithm fails to converge, the following structures will be executed: heterogeneous Toeplitz, heterogeneous First-Order Autoregressive [AR (1)], heterogeneous compound symmetry (HCS), Toeplitz, AR(1), and compound symmetry (CS). The covariance structure converging to the best fit, as determined by Akaike's information criterion (AIC, the smaller the AIC value the better the model fit), will be used. If the model converges with an unstructured covariance matrix, the Kenward and Roger method will be used to calculate the denominator degrees of freedom for the test of fixed effects. If a structured covariance is used, then a robust sandwich estimator will be utilized for estimating the variance of the treatment effect estimate.

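### The minimum-data rule for PD AUCs can drop the best-suppressed VAP-1/SSAO profiles; Aavg, Cavg and the Week 12 interval for Amax also need defining

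*SAP*

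**What the plan says.** **AUC rule.** SAP 8.8.4.2 makes it a minimum requirement for any PD AUC that the profile contains "at least three consecutive plasma VAP-1/SSAO activity or methylamine concentrations above the LLOQ". SAP 8.8.4.3 then says that "all NR and not calculated (NC) values in a data series will be set to missing" for the summaries. SAP 8.8.1 separately assigns half the quantification limit to PD values that are BLQ, so every such sample already has a number. Table 8 defines AAUCtau over 0 to 24 hours by the linear trapezoidal rule.

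**Averages.** Table 8 describes Aavg as an average of the value, change and "percent change from baseline at steady state (Week 6 and Week 12 only"). Table 9 describes Cavg as "Average observed methylamine concentration (and separately, change and percent change from baseline) at steady state (Week 6 and Week 12 only"). Neither gives a formula or an interval. SAP 8.8.4.3 names Aavg and Amin, and Cavg and Cmax for methylamine, under "Analyses of pre-dose/trough values for plasma VAP-1/SSAO activity", and says that the analyses "at Week 0/Day 1, Week 6, and Week 12 will be carried out using an ANCOVA model". SAP 8.8.4.4 uses the same label: dose response is "based on the pairwise comparisons of pre-dose/trough values for plasma VAP-1/SSAO activity".

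**Week 12 samples.** SAP 8.8.4 stops the Day 1 and Week 6 profiles at the next dose, but "Week 12 will include pre dose and all post dose assessments". Protocol 1.3 and Appendix 2 place those at up to 72 h after the last dose. Table 8 does not confine Amax or ATmax to the dosing interval, and Table 9 does not confine the methylamine minimum or its time.

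**The concern.** The PK section (SAP 8.7.4.2) has a similar three-value rule. It suits PK, where a BLQ value means little drug. For enzyme activity the meaning reverses: a BLQ value means near-complete inhibition. The rule therefore makes AAUCtau missing because the drug worked, and the patients who remain in the summary are the less suppressed ones. The condition is plausible. Protocol 2.2.2 reports more than 90% inhibition at 10 mg in healthy participants, sustained over repeat dosing, and SAP 8.8.2 already plans for time points at which all PD values are BLQ.

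Methylamine rises with inhibition (protocol 2.2.2), so there the rule would remove low profiles, mainly placebo or the least suppressed patients.

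The two definition problems do not depend on the LLOQ. Two programmers could derive different values of Aavg and Cavg, which are modelled parameters. Week 12 Amax could also describe recovery after treatment rather than the dosing interval.

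**Working it through.** The plan states no figure to reproduce, and neither document gives an LLOQ.

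**Inputs from the documents.** There are eight samples over 0-24 h: pre-dose, 0.5, 1, 2, 4, 6, 8 and 24 h (protocol 1.3). Residual activity was below 10% of baseline at 10 mg in healthy participants (protocol 2.2.2). The sub-study has about 8 patients at 10 mg and 6 at each Part 2 dose (SAP 2.2); protocol 6.4 gives 6 at 10 mg.

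**Assumptions.** Activity is log-normal, as a percentage of baseline, with CV 60% between and 30% within patients. The median residual is 10% or 5%, and the LLOQ is 2, 5 or 10% of baseline. I simulated 200,000 profiles per scenario.

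**Rule logic.** A profile with all eight samples BLQ has no AAUCtau. One with six of eight quantifiable also fails if they fall as two above, one below, two above, one below, two above. With half-LLOQ values and an LLOQ of 5%, the all-BLQ profile has AAUCtau = 24 x 2.5 = 60 %·h, a mean residual of 2.5%. The rule discards it.

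**True mean residual** = median x sqrt(1 + 0.6²) x sqrt(1 + 0.3²) = median x 1.2175, that is 12.2% for a median of 10% and 6.1% for 5%.

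**Under the current rule**, understatement = mean AAUCtau/24 of the kept profiles minus the true mean:

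| Median residual | LLOQ | Profiles lost | Kept mean | Suppression understated by | Fewer than 3 AUCs left, n = 8 / n = 6 |
|---|---|---|---|---|---|
| 10% | 2% | 0.3% | 12.2% | under 0.1 points | under 1% / under 1% |
| 10% | 5% | 13% | 13.2% | 1.0 points | under 1% / under 1% |
| 10% | 10% | 52% | 17.1% | 4.9 points | 17% / 38% |
| 5% | 2% | 6% | 6.4% | 0.3 points | under 1% / under 1% |
| 5% | 5% | 52% | 8.6% | 2.5 points | 17% / 38% |
| 5% | 10% | 90% | rarely reported | missing summary | 96% / 98% |

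The last column is binomial. At 52% loss and n = 8: 0.52⁸ + 8 x 0.48 x 0.52⁷ + 28 x 0.48² x 0.52⁶ = 0.005 + 0.039 + 0.128 = 0.17. With fewer than three values, SAP 4.1 prints only N, minimum and maximum.

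**Sensitivity** (residual 5%, LLOQ 5%): CVs of 40-80% between and 20-40% within patients give 51-54% lost and 1.5 to 3.6 points.

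**Methylamine**, same CVs: if the placebo median is 1, 1.5, 2 or 3 times the LLOQ, then 52, 26, 13 or 3% of placebo profiles are lost, and the placebo mean AUC is overstated by about 40, 18, 9 or 2%.

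**Keeping every profile with half-LLOQ values**: the error is -0.7 to +0.2 points for LLOQ up to 10%. With residual 5%, it is +1.9 points at an LLOQ of 15% and +4.1 at 20%. Setting BLQ to 0 and to the LLOQ brackets the true mean in every scenario; for residual 5% and LLOQ 5% the bounds are -1.6 and +0.9 points.

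**Aavg and Cavg side by side.** Tables 8 and 9 restrict them to Weeks 6 and 12, while 8.8.4.3 also models them at Day 1. An interval average is not a trough. If they are trough values, the AUC rule does not reach the ANCOVA; if they are AAUCtau/24, it does.

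**Amax.** A maximum over 0-72 h cannot be lower than one over 0-24 h, so returning activity can only raise the Week 12 value. No document gives a recovery rate, so I attach no size.

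**The case against.** The strongest reply concerns size and reach. The LLOQ is unknown. Protocol 4.3 expects higher baseline VAP-1 in NASH patients, so a fixed LLOQ would be a smaller share of their baseline, although it also says that the PD effect may differ. If the LLOQ is well below residual activity, almost nothing is lost. AAUCtau is in no named inferential model: 8.8.4.3 and 8.8.4.4 name Aavg, Amin, Cavg and Cmax. Testing is nominal (8.6), and the BLQ counts (8.8.2) and N would reveal a loss. All of this stands and limits the point. It does not alter the direction of the loss, and disclosure does not correct it.

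A reader might infer four stronger things, which the documents do not support:

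- **Reported suppression could be wrong by 7 points or more.** At residual 5% and LLOQ 10% the kept mean is 7.2 points too high, but fewer than three AUCs would remain in at least 96% of cases, so SAP 4.1 would withhold that mean.
- **Weeks 6 and 12 would rest on different patients, because the 24, 48 and 72 h samples can satisfy the rule at Week 12.** The natural reading is that the three values must lie in the AUC being calculated, and Table 8 fixes that at 0-24 h. Any size would also need an assumed recovery rate.
- **Late samples distort PK Cmin and Tmin.** Table 6 already limits these to steady state. Aavg and Cavg carry the same words, which arguably keep late samples out.
- **The secondary endpoint is biased.** Percent change in activity is analysed by time point (8.8.3), without the AUC rule. Amin and the MMRM do not use it either, and the Part 2 criteria in 8.3 do not name AAUCtau.

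**Conclusion.** The concern holds in a limited form and is minor. The AUC rule loses AAUCtau selectively in strongly suppressed patients, and it is unnecessary because BLQ samples already have assigned values. Where a mean would usually be reported, the understatement is about 0 to 5 points, conditional on the assumed LLOQ, residual activity and CVs. Where most profiles are lost, the result is a missing summary rather than a biased one. The effect is confined to AAUCtau and methylamine AUCtau summaries in the sub-study and to any exposure-response model that uses them, since SAP 8.9 refers only to PD parameters in general. It would extend to the ANCOVA only if Aavg or Cavg is derived from the AUC.

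The Aavg/Cavg conflict and the open Week 12 interval for Amax and ATmax stand on the text alone, without any assumption about the assay.

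**What to change.** - **SAP 8.8.4.2:** drop the condition on values above the LLOQ for PD AUCs. Require enough non-missing samples to cover 0-24 h: pre-dose, 24 h and at least one between. A bare count of three would not do, because pre-dose, 0.5 h and 1 h would qualify and leave 23 of the 24 hours unobserved. Use half the LLOQ for BLQ samples, as in 8.8.1. Flag AUCs that rest mainly on imputed values; if any are flagged, repeat the summary with BLQ set to 0 and to the LLOQ.
- **SAP 8.8.4:** derive Week 12 Amax, ATmax and the methylamine extremes from 0-24 h, as at Week 6. Summarise the 48 h and 72 h samples separately as recovery.
- **Tables 8 and 9:** give the formula for Aavg and Cavg, over 0-24 h, and reconcile the tables with the trough label and the Day 1 analysis in 8.8.4.3 and 8.8.4.4.

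The cost is SAP wording and some programming, with no new data. There are two downsides. AUCs of fully suppressed patients will depend on the half-LLOQ value, which overstates activity if the LLOQ is far above it; the flag and the bounds show this. A patient without a 24 h sample would have no PD AUC, because 8.8.4, unlike 8.7.4, has no rule for reusing the pre-dose value.

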#### **8.8.4.3. Statistical Methods for PD Parameters**

Plasma PD parameters will be summarized by treatment group using descriptive statistics (number of non-missing observations, arithmetic mean, SD, median, Q1, Q3, minimum, maximum, geometric mean, and geometric CV%).

For the calculation of summary statistics, all NR and not calculated (NC) values in a data series will be set to missing.

Analyses of pre-dose/trough values for plasma VAP-1/SSAO activity ( $A_{avg}$  and  $A_{min}$ ) and methylamine ( $C_{avg}$  and  $C_{max}$ ) at Week 0/Day 1, Week 6, and Week 12 will be carried out using an ANCOVA model with the PD parameter as the dependent variable including treatment group as a fixed effect and baseline VAP-1/SSAO activity or methylamine concentration as a covariate. The model will be carried out separately for the PD parameter based on the VAP-1/SSAO activity and methylamine value, change from baseline, and percent change from baseline. The estimates of LS means, SE, and 90% and 95% CIs will be presented by treatment group. Estimates of the LS mean difference for each pairwise comparison will be presented with associated the standard error of the difference, and 90% and 95% CIs of the difference.

The distribution of parameter values will be evaluated visually for normality assumptions. If normality assumptions are violated, first the data will be natural log transformed and the log transformed data evaluated for normality. If the log transformed data are normally distributed, the same ANOVA model described above will be used.

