#### 4.7.2. Definition of Baselines

The baseline value for statistical analyses of quantitative laboratory parameters is defined as the mean of all available evaluations, including any unscheduled or repeat assessments, prior to the first administration of study drug, unless otherwise specified. If there is only one evaluation prior to the first administration of study drug, then the available data from this evaluation will be used as the baseline value.

For glucose and lipid parameters, only assessments taken while fasting for at least 8 hours will be included in the baseline derivation.

The baseline value for analyses of qualitative parameters (e.g., normal/abnormal) is defined as the last evaluation prior to the first administration of study drug.

The baseline value for analyses of height, weight, body mass index (BMI), waist circumference, and electrocardiogram parameters is defined as the last evaluation prior to the first administration of study drug.

The baseline value for pharmacodynamic analytes is defined as the Week 0/Day 1 predose value.

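### SAP 8.8.4.3 and 8.8.4.4 call the ANCOVA outcome a pre-dose/trough value but name sub-study profile parameters, two of which do not exist at Week 0/Day 1

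*SAP*

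**What the plan says.** SAP 8.8.4.3 specifies an ANCOVA for "Analyses of pre-dose/trough values for plasma VAP-1/SSAO activity" (Aavg and Amin) and methylamine (Cavg and Cmax) at Week 0/Day 1, Week 6 and Week 12. Treatment group is the factor and baseline the covariate. The model is run separately for the value, the change and the percent change. SAP 8.8.4.4 then allows dose-response to be evaluated "based on the pairwise comparisons of pre-dose/trough values for plasma VAP-1/SSAO activity" and methylamine from those models, and plots the same quantities under the same label.

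The named parameters are defined elsewhere:

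- SAP 8.8.4: "Plasma PD parameters will be computed for PK/PD sub-study patients only".
- SAP Table 8, Amin: "Minimum observed VAP-1/SSAO activity, calculated separately for the value, change from baseline, and percent change from baseline", read from the activity-time profile, with no limit on visits. Table 9 defines methylamine Cmax in the same way, as a maximum.
- SAP Table 8, Aavg: the entry carries the restriction "at steady state (Week 6 and Week 12 only").
- SAP Table 9, Cavg: "Average observed methylamine concentration (and separately, change and percent change from baseline) at steady state (Week 6 and Week 12 only").
- SAP 4.7.2: "The baseline value for pharmacodynamic analytes is defined as the Week 0/Day 1 predose value".

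Two other analyses bear on the point. SAP 8.8.3 assigns trough time points to the PD Analysis Set. It specifies an ANCOVA by time point on change and percent change, with pairwise LS mean differences. SAP 8.8.4.4 also specifies an MMRM on change and percent change, tied to none of these parameters and with no analysis set stated.

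**The concern.** A trough is a single pre-dose sample, which Protocol Appendix 2 (Table 3) schedules for every patient. None of the four named parameters is a trough: two are profile averages and two are profile extremes. The label and the parameters therefore point to different outcomes, patients and visits, and a programmer would have to choose between them. The mismatch recurs in 8.8.4.4 for both the comparisons and the plots, so it is not a single slip.

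Two things are at stake. Part of the Day 1 analysis cannot be run as written. And the pairwise dose-response comparison could end up on about a third of the patients, although the same question can be answered from samples taken in all of them.

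**Working it through.** **1. Day 1 under each reading**

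- *Profile parameters as named.* Four parameters at three visits give 4 × 3 = 12 analyses. Aavg and Cavg at Day 1 are excluded by Tables 8 and 9, so 2 of 12 have no data. Amin and Cmax carry no visit restriction, so the other 10 can be run. A Day 1 Amin percent-change ANCOVA on simulated data gave ordinary non-zero estimates and standard errors.
- *Literal Day 1 pre-dose sample.* By SAP 4.7.2 this is the baseline, so outcome = covariate. Change = baseline − baseline = 0 for every patient, and percent change = 0. For the raw value, the baseline slope is 1, every treatment effect is 0 and the residual sum of squares is 0. A fit to simulated data gave about 1e-27, which is zero to numerical precision.

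**2. Planned sub-study sizes, reproduced**

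- Part 1 (SAP 2.2): 8 active + 4 placebo = 12, as stated.
- Part 2 (SAP 2.2): 6 + 6 + 3 = 15, as stated.
- Whole study: 30 + 50 = 80, or 20 at each of three doses and 10 + 10 = 20 placebo, pooled under SAP 4.6.

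The sub-study therefore has 6 at 4 mg, 8 at 10 mg, 6 at 20 mg and 4 + 3 = 7 pooled placebo. That is 27 of 80 (33.8%), leaving 53 (66.3%) unused.

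Protocol 6.4 gives the Part 1 sub-study as 6 active and 6 placebo. The total is still 27, but 10 mg becomes 6 and pooled placebo 6 + 3 = 9.

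**3. Effect on precision**

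SE ratio = √[(1/a + 1/b) / (1/20 + 1/20)], where a and b are the sub-study group sizes and the residual SD is taken as equal for the two outcomes.

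| Comparison | a v b (8:4 split) | SE ratio | a v b (6:6 split) | SE ratio |
|---|---|---|---|---|
| 4 mg or 20 mg v placebo | 6 v 7 | 1.76 | 6 v 9 | 1.67 |
| 10 mg v placebo | 8 v 7 | 1.64 | 6 v 9 | 1.67 |
| 4 mg or 20 mg v 10 mg | 6 v 8 | 1.71 | 6 v 6 | 1.83 |
| 4 mg v 20 mg | 6 v 6 | 1.83 | 6 v 6 | 1.83 |

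For example, √[(1/6 + 1/7)/0.1] = √3.095 = 1.76.

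The equal-SD assumption matters, because a profile average may vary less between patients than a single trough. To offset the smaller sample against placebo (8:4 split), its SD would have to be 1/1.76 = 0.57 to 1/1.64 = 0.61 of the trough SD, that is, 39% to 43% lower.

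**The case against.** The strongest reply is that 8.8.4.3 is headed as methods for PD parameters, sits under a section limited to the sub-study, and calls its outcome the PD parameter. On that reading the trough label is a stray phrase and 10 of the 12 analyses run. This stands. A reader might infer that no reading of 8.8.4.3 works, or that the whole Day 1 analysis is lost. The documents do not support either: Amin and Cmax are defined on Day 1. There is also a 24-hour sample after the first dose in the sub-study, and modelling it would not be degenerate. However, that sample is not one of the named parameters and is not taken in all patients.

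Second, the all-patient trough comparison is already planned in 8.8.3 with pairwise differences and 90% and 95% confidence intervals, and the MMRM in 8.8.4.4 is not tied to the sub-study parameters. This also stands. It would be wrong to conclude that the study loses its all-patient PD comparison, or that every dose-response route loses most patients. The loss concerns only the pairwise ANCOVA route, and only if the named parameters are used. That route is conditional on Part 2 enrolling and on the data warranting it, and SAP 8.6 makes all testing nominal and exploratory.

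Third, one might add that Amin is biased as a contrast, because a minimum over noisy samples shows some suppression on placebo. The size of that effect depends on a within-patient CV that the documents do not give, and maximum suppression is a legitimate PD quantity. It is not needed for this point.

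What the reply does not remove is the conflict between label and parameters, or the two Day 1 analyses with no data.

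**Conclusion.** The point holds in this limited form. The outcome in 8.8.4.3 and 8.8.4.4 is labelled as one quantity and named as another. Two of the twelve parameter-by-visit analyses have no data, and the literal pre-dose reading of Day 1 is degenerate. If the named parameters are used, the 8.8.4.4 pairwise route rests on about 27 of 80 planned patients. Standard errors against pooled placebo are then 1.64 to 1.76 times those from all-patient troughs, or 1.67 under the 6:6 split in Protocol 6.4; between doses they are 1.71 to 1.83 times as large.

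These figures assume the approximate planned numbers, both Part 2 doses enrolled, no dropout and equal residual SDs. The primary safety endpoint and the 8.8.3 analysis of VAP-1/SSAO activity are untouched. The point is still worth correcting before unblinding, because it leaves outcome, population and visits to the programmer. Precision is likely to matter most between doses: Protocol 2.2.2 reports more than 80% inhibition at 1 mg and more than 90% at 10 mg after a single dose in healthy participants, so differences between doses may be small. Protocol 4.3 cautions that the effect in NASH patients may differ.

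**What to change.** 1. In SAP 8.8.4.4, base the pairwise dose-response comparisons and the plots on the 8.8.3 ANCOVA of trough activity and methylamine, in the PD Analysis Set, at post-baseline visits only (Weeks 2, 4, 6, 8 and 12). This fits the dose-group ANCOVA in Protocol 9.4.3.2, which is not restricted to the sub-study. The 8.8.3 model includes the randomization strata and the 8.8.4.3 model does not, so say which applies. State the analysis set for the MMRM as well.
2. In SAP 8.8.4.3, delete the pre-dose/trough label and state that the outcomes are profile parameters in the PK/PD sub-study. Limit Aavg and Cavg to Weeks 6 and 12. If a Day 1 average is wanted, use the 0–24 h AUC divided by 24, which the Day 1 sampling supports, subject to the minimum-data rule in SAP 8.8.4.2. Amin and Cmax may stay as secondary sub-study parameters.
3. Reconcile the Part 1 sub-study split (8:4 in SAP 2.2 and Protocol 4.1, 6:6 in Protocol 6.4).

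The cost is SAP wording and table shells, plus a correction to the protocol text if 6.4 is the part in error. Every sample needed is already scheduled.
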